##### **SAFETY GOALS**

**Primary Safety Endpoints:** Procedure freedom from Serious Adverse Events (SAEs) during the ePTFE implantation procedure, at discharge, and at 30 days follow-up shall be tracked and recorded.

**Secondary Safety Endpoints** Freedom from Serious Adverse Events (SAEs) at 6 months, 12 months, 18 months, 24 months, 30 months and, 36 months follow-up shall be tracked and recorded.

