#### PATIENT WITHDRAWAL FROM THE STUDY

A withdrawal refers to a patient who is determined to be inactive in the study due to physician discretion, patient or family choice (if the patient becomes incapacitated and is unable to continue with the study due to a family choice), and loss to follow-up or patient death. Final status shall be reported on all patients as per the informed consent. Three documented phone calls and a registered/certified letter shall be used to assure that there is minimal loss to follow-up. If these efforts to contact the patient are unsuccessful, the patient shall be considered lost to follow-up.

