## TREATMENT PROCEDURE/ASSESSMENTS

The procedural approach requires that the patient be administered a general (single lumen) endotracheal anesthesia with appropriate monitoring lines (e.g. arterial line) and heparinised saline to achieve an activated clotting time of  $\geq 350$  seconds. The patient should be placed in the supine position with elevation of the left hemithorax to 30°. Briefly, the procedure consists of performing a small left lateral thoracotomy incision overlying the left ventricular apex, opening the pericardium and selecting an insertion site on the epicardium for the Harpoon Medical device where a monofilament purse-string suture is placed to hold the Harpoon device introducer in place and reduce bleeding. Once the introducer is in place, the device is inserted and positioned adjacent to the mitral leaflet under TOE guidance and bulky suture knot is deployed to secure paired sutures in the leaflet. The paired sutures are brought outside the ventricle. Up to four (4) suture pairs may be placed, using a singled valved introducer, to secure and align apposition between the anterior and posterior mitral leaflets. If more than four (4) suture pairs are required, the valved introducer must be removed and reinserted for reuse, and then an additional four (4) suture pairs may be inserted. Once an adequate number of suture pairs are placed, the device and introducer are removed, and the suture pairs are tightened and secured to the exterior myocardium using pledges for each suture pair. The thoracotomy should be closed, and chest tube(s) should be inserted, per hospital standard of care.

The details of the procedure are described thoroughly in the Harpoon Medical device Instructions for Use.

If in the judgment of the operating surgeon, adequate MR reduction has not been achieved, or if for any other clinical reason, conversion to SOC mitral valve surgery via a median sternotomy shall be performed. This procedure may be performed at the time of the Harpoon Medical TRACER procedure or at a later date/time at the discretion of the operating surgeon. Subjects who undergo a conversion to SOC mitral valve surgery via a median sternotomy will be followed up for 30 days.

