## FOLLOW-UP PROCEDURES/ASSESSMENTS

**Post-procedure management:** Standard hospital protocols for the management of patients after mitral valve surgery shall be followed. Unless other indications for anticoagulation are present, all patients shall receive only 325 mg/day, beginning on arrival to the intensive care unit).

**Discharge:** All patients shall be discharged from the hospital at the discretion of the attending cardiac surgeon. Prior to dismissal all patients shall undergo a comprehensive pre-dismissal TOE, as well as a physical assessment (vide supra) in accordance with the schedule of Clinical Investigations.

**Patient follow-up:** Patients shall be seen in the outpatient clinic 30 days (+10 days/-0 days) after the Harpoon procedure. A TTE and a clinical assessment shall be performed at that time (in accordance with the schedule of Clinical Investigations) to evaluate the device against the primary and secondary performance and safety endpoints.

Additional clinical and TTE follow-up in a registry fashion shall occur for all active subjects (in accordance with the Clinical Investigations defined in the table below) at the following intervals:

- 6 months (+/- 30 days),
- 12 months (+/- 30 days)
- 18 months (+/- 30 days)
- 24 months (+/- 30 days)
- 30 months (+/- 30 days)
- 36 months (+/- 30 days)
- 48 months (+/- 30 days) and
- 60 months (+/- 30 days)

If due to an increase of MR, or due to any other medical circumstances, and a study patient has to undergo a Mitral Valve reoperation, this patient will be followed up by the study team for 30 days and then will be exited from the study

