Freedom from Serious Adverse Events (SAEs) during the ePTFE implantation procedure, at discharge, and at 30 days follow-up will be tabulated. The number of patients experiencing one or more AEs or SAEs at 30-days post-procedure, the percentage of patients, and the exact 95% confidence limit will be calculated. Patients who die prior to 30 days will be considered failures for this analysis.

Freedom from Serious Adverse Events (SAEs) at 6 months, 12 months, 18 months, 24 months, 30 months and 36 months follow-up shall be tabulated. The number of patients experiencing one or more AEs or SAEs at 6 months, 12 months, 18 months, 24 months, 30 months, 36 months, 48 months and 60 months follow-up, the percentage of patients, and the exact 95% confidence limit will be calculated.

These data shall be used to assess the safety and performance of the Harpoon Medical device, and are not designed to test a statistical hypothesis, and therefore a formal sample size has not been calculated. All data shall be captured on an intent-to-treat basis. Data shall be reported as descriptive statistics.

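### SAE percentages from 6 to 60 months have no denominator or censoring rule, so they are biased whenever patients leave event-free; Kaplan-Meier should be the main estimate after 30 days

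*Combined protocol and SAP*

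**What the plan says.** All references are to the combined protocol and SAP.

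- **Endpoint.** Section IV, Safety Goals, sets the secondary safety endpoint as "Freedom from Serious Adverse Events (SAEs) at 6 months, 12 months, 18 months, 24 months, 30 months and, 36 months follow-up". Section X matches it: "Freedom from Serious Adverse Events (SAEs) at 6 months, 12 months, 18 months, 24 months, 30 months and 36 months follow-up shall be tabulated".
- **Counts and limits.** Section X also plans the number of patients with one or more AEs or SAEs at each visit from 6 months on, ending with "48 months and 60 months follow-up, the percentage of patients, and the exact 95% confidence limit will be calculated". It does not say whether a figure at a visit is cumulative or covers the time since the previous visit.
- **Rules for incomplete follow-up.** For SAEs there is one, at 30 days: "Patients who die prior to 30 days will be considered failures for this analysis". The nearest text to a denominator is "All data shall be captured on an intent-to-treat basis". The last-observation and tipping-point rules in Section X concern MR up to 30 days.
- **How observation ends.** On conversion: "Subjects who undergo a conversion to SOC mitral valve surgery via a median sternotomy will be followed up for 30 days" (Section VII, Treatment Procedure). On mitral reoperation: "this patient will be followed up by the study team for 30 days and then will be exited from the study" (Section VII, Follow-up). Section VI is wider: "A withdrawal refers to a patient who is determined to be inactive in the study due to physician discretion", with patient or family choice, loss to follow-up and death also listed. Under Section VIII, Retrospective Collection of Data, the added visits need new consent, and patients who had already exited at 36 months are to be approached again.

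**The concern.** Freedom from SAE by month t is a time-to-first-event quantity. A count over a fixed number of patients, with exact binomial limits, estimates it properly only if every patient without an SAE has been observed to month t. Three denominators are compatible with the text, and each behaves differently once someone leaves event-free:

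- **All enrolled:** the patient who left counts as SAE-free for years not observed, so SAE freedom is too high.
- **Event or complete follow-up:** event-free time is thrown away while events are kept, so SAE freedom is too low.
- **Patients attending the visit:** those who exited after conversion or reoperation drop out together with the SAE that led to the exit, so SAE freedom is too high.

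Because the plan does not choose, the choice can be made after the data are seen. The long-term safety description of the device, which this amendment extends to five years, rests on these figures.

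**Working it through.** The documents give no SAE rate, exit rate or sample size for this analysis, so there is no figure of the plan's to reproduce. All rates below are assumptions. The sizes used are n = 30 (the CE-mark set, Section X) and n = 80 (four countries of up to 20, Study Summary).

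**One data set, several answers.** Suppose 30 patients and 12 first SAEs: 8 before about 18 months, 2 between about 20 and 36 months, 2 after 36 months. Six patients leave event-free: 2 at about 18-20 months and 4 at 36 months. Five of the SAE patients have exited by 60 months.

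- All enrolled: 18/30 = 60.0% (exact limits 40.6-77.3).
- Event or complete: 12/24 = 50.0% (29.1-70.9).
- Attenders: 12/19 = 63.2% (38.4-83.7).
- Kaplan-Meier: 22/30 × 18/20 × 12/14 = 56.6% (log-log limits 35.7-73.0).

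If the six had stayed without an event, Kaplan-Meier and 18/30 would both be 60.0%.

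**Expected bias.** Let p be the probability of a first SAE by 30 days, λ the yearly hazard after that, c the yearly exit hazard independent of SAE, s the share stopping at 36 months, and T the time in years.

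- True SAE-free rate: S = (1-p)·exp[-λ(T-1/12)]
- Observed events, no stop: E(T) = p + (1-p)·λ/(λ+c)·{1-exp[-(λ+c)(T-1/12)]}
- Event-free completers, no stop: C(T) = (1-p)·exp[-(λ+c)(T-1/12)]
- With a stop at 36 months, at T = 5: E = E(3) + (1-s)·C(3)·λ/(λ+c)·[1-exp(-2(λ+c))], and C = (1-s)·C(3)·exp[-2(λ+c)]
- All-enrolled rate: 1-E. Event-or-complete rate: C/(C+E).

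Central setting (p = 0.15, λ = 0.08, c = 0.05, s = 0.20):

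- 36 months: S = 0.673, E = 0.315, C = 0.582. All enrolled 0.685 (+1.2 points); event or complete 0.582/0.897 = 0.649 (-2.4).
- 60 months, s = 0: S = 0.574, E = 0.397, C = 0.449. Rates 0.603 (+2.9) and 0.530 (-4.3).
- 60 months, s = 0.20: E = 0.381, C = 0.359. Rates 0.619 (+4.6) and 0.485 (-8.8).

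Bias in points, all enrolled / event or complete:

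| p, λ, c, s | 36 months | 60 months, s = 0 | 60 months, with s |
|---|---|---|---|
| 0.15, 0.06, 0.03, 0.10 | +0.6 / -1.4 | +1.5 / -2.5 | +2.2 / -4.6 |
| 0.15, 0.08, 0.05, 0.20 | +1.2 / -2.4 | +2.9 / -4.3 | +4.6 / -8.8 |
| 0.20, 0.10, 0.05, 0.30 | +1.3 / -2.7 | +3.2 / -4.5 | +5.9 / -11.7 |

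Simulated Kaplan-Meier means at 60 months with the stop are 0.630, 0.575 and 0.489, against true values of 0.633, 0.573 and 0.489.

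**Coverage of the exact 95% limits (simulation).** At n = 30 it is about 96-97% at 36 months and about 94-97% at 60 months with full re-consent. With the stop at 36 months it is 93-96% for all enrolled and 87-95% for event or complete. At n = 80, in the central setting with the stop, it falls to about 87% and 77%.

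**Attenders.** A separate simulation (n = 30, true 60-month rate 60%, 40% of first SAEs followed by exit about 30 days later) had no event-free exits at all. The all-enrolled mean was 60.0% with 96.4% coverage. The attender mean was 71.3% with 84.7% coverage.

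**The case against.** The strongest reply is that the exits most clearly built into the protocol are themselves events. Conversion, reoperation and death would normally meet the SAE definition in Section VIII, which covers death, hospitalisation or its prolongation, and certain surgical interventions. A cumulative all-enrolled count already scores those patients as failures. This stands. A reader might infer that the percentages are wrong whichever denominator is used; the documents do not support that, because with no event-free exits the all-enrolled figure agrees with Kaplan-Meier. The bias comes from withdrawal, loss and missing re-consent, and the documents put no number on any of them.

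A reader might also infer that the confidence limits are wrong. At n = 30 that is not shown for modest attrition. The exact interval around 18/30 spans about 18 points each way, so a bias of 1 to 4 points is small beside sampling error. Coverage falls clearly below 95% only with heavier assumed attrition or larger n.

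The endpoint and the SAE-freedom tabulation stop at 36 months. Only the AE/SAE counts run to 60 months, so a five-year SAE-free rate is not a named endpoint. Section X also calls the analysis descriptive, with no hypothesis to test. Both points limit the stakes. They do not remove the concern: Section X says these data will be used to assess safety and performance, and a descriptive figure should still have a defined meaning.

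Finally, Kaplan-Meier assumes that exit carries no information about later SAEs, and self-selected re-consent may break that. This is a fair caution for the fix.

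**Conclusion.** The concern holds conditionally. The plan leaves the denominator, the cumulative or interval meaning and the handling of event-free exits undefined. Once any patient leaves event-free before the time point, none of the three simple denominators can be relied on to be unbiased. The attender version can mislead even without such exits, because it hides SAEs that led to exit.

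For the all-enrolled and event-or-complete rates the likely error is small at the 36-month endpoint and moderate at 60 months. It becomes large, up to about 6 points too high or 12 too low, only if a sizeable share does not continue past 36 months. These sizes rest on assumed rates: 15-20% first SAE by 30 days, 6-10% a year after that, 3-5% a year exit, 0-30% stopping at 36 months, and exit independent of SAE.

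**What to change.** In Section X, for time points after 30 days:

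- Make Kaplan-Meier freedom from first SAE the main estimate, with log-log 95% limits and numbers at risk at each visit. Time runs from the procedure.
- Count death as an event, and conversion or reoperation where it meets the SAE definition. Censor everyone else at last documented contact.
- Keep the planned counts and percentages beside it. State the denominator of each, and whether it is cumulative or covers the interval since the last visit.
- Keep the exact binomial summary at 30 days.
- List all exits with date and reason, separating non-consent to the extension, so that a reader can judge whether censoring is plausibly non-informative.

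The cost is analysis wording and one program. Event onset dates (Section VIII, Reporting Adverse Events) and visit and exit dates with the reason for discontinuation (Section XI, Source Documentation) are already recorded. The limitation is the non-informative-exit assumption; the listing exposes it but does not cure it.

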## **XI. STUDY ORGANISATION**

### **INVESTIGATIONAL SITE PERSONNEL**

#### **Investigator and co-investigators**

The Investigator is responsible for ensuring that this trial is conducted according to this protocol and that signed Informed Consent is obtained from each patient prior to their inclusion in this trial.

It is the Investigator's responsibility to ensure that all staff assisting with this trial have the appropriate qualifications and are fully instructed on the trial procedures and respect patient confidentiality, as specified in the Investigator Agreement with the Sponsor.

The Investigator is responsible for ensuring that the conduct of the trial conforms to the EC and Competent Authority (CA) requirements and provides all necessary communication with the EC and CA including, but not limited to, annual trial reports and required adverse event notifications. Specific responsibilities:

- An Investigator shall conduct an investigation in accordance with the signed Investigator Agreement with the Sponsor, the Protocol, applicable international regulations, and any conditions of approval imposed by a local regulatory body, Ethical Committee (EC), or Competent Authority.
- The standardised Case Report Forms (CRFs) will be used to collect complete and accurate records of the clinical data from the trial according to the International Conference on Harmonisation (ICH)/WHO Good Clinical Practice (GCP) standards. The Investigator is responsible for collecting and accurately recording the data generated for this trial.
- Investigators will maintain a screening log that will record the date of informed consent, the date of screening, the enrollment status (enrolled/excluded) and the reason for exclusion for all screen failures.
- A participating Investigator shall maintain accurate, complete, and current records (listed in detail in the Investigator Agreement) relating to the Investigator's participation in the trial for a period of 10 years or longer, as may be required by applicable laws, rules and regulations.
- An Investigator shall prepare and submit complete, accurate, and timely reports on adverse events, withdrawal of EC approval, progress, deviations from the protocol, informed consent, termination or completion of the trial, and other trial-related aspects requested by the EC, Competent Authority or Sponsor representative. (These are described in more detail in the Investigator Agreement.)

The Sponsor reserves the right to terminate this study at a given site or across all sites if any of the following situations occur:

- The rate at which patients are being entered into the study is insufficient as determined by the Sponsor;

- Protocol compliance is poor as measured by the number of reported and monitored protocol deviations and violations;
- Data recording is inaccurate or incomplete on a chronic basis;
- The incidence and/or severity of adverse events related to the use of the study device indicate a potential increased risk to the safety and welfare of trial patients;
- The Sponsor and/or the local Competent Authority mandate the termination of the study.

#### Study Coordinator

Each site in the Mitral TRACER Trial is required to identify a Study Coordinator who will be responsible for, but not limited to, the following:

- Scheduling diagnostic and assessment procedures.
- Informing all study team members of scheduled treatments.
- Paging study team members on the morning of scheduled treatments to ensure that all necessary personnel will be present.
- Entering all study data into the Case Report Forms.
- Maintaining a list of all patients screened for the trial and those who have entered the trial and their patient numbers.
- Maintaining the Device Accountability Log.
- Scheduling all follow-up visits within the appropriate follow-up windows and ensuring that all follow-up data is collected in accordance with the protocol.

#### CLINICAL MONITORING

The clinical trial site(s) shall be monitored in accordance with policies at Harpoon Medical, Inc. and those federal regulations that pertain to clinical research; namely, ISO-14155, 21 CFR Parts 50, and 56; and others as applicable.

The Sponsor or its designated representative, qualified by training and experience, will be responsible for monitoring and overseeing the conduct of the trial. These responsibilities include maintaining regular contact with each Investigational site and conducting on-site monitoring visits at the Investigational site to ensure compliance with this Protocol, to verify that accurate and complete data are being submitted in a timely manner, and to verify that the Investigational site facilities continue to be adequate.

Monitors are responsible for assuring that each Investigator and his/her staff clearly understand and accept their obligations under the clinical investigation through site visits, written communications and phone calls between the Monitor and the Principal Investigator and staff.

During the course of the investigation, the Monitor shall assure that the Principal Investigator and his/her staff:

- Understand and agree to the requirements of the protocol;

- Agree to their obligations to conduct the study;
- Accept the obligation to obtain informed consent using the Patient Information Sheet approved by the REC;
- Have access to an adequate number of suitable patients to conduct the investigation;
- Have facilities adequate to conduct the clinical investigation; and
- Have sufficient time to fulfill his/her obligations under the study;

During the course of a clinical investigation, the Monitor shall periodically visit the clinical investigation site to assure that:

- Changes to the protocol have been approved by the ethics committee and reported to Sponsor, Inc. and the EC;
- Adverse events (anticipated and unanticipated) are recorded and reported in accordance with the spirit of Good Clinical Practices (GCPs), ISO-14155-1, Declaration of Helsinki, and as per the Investigator Agreement;
- Accurate, complete, and current records are being maintained;
- Patient confidentiality of records and study participation are being maintained; and
- Accurate, complete and timely reports are being made to Sponsor and to the EC.

Patient information shall remain confidential. Should any new knowledge about the patients' medical condition become known, it will be dealt with in the usual confidential fashion. Any data that may be published in scientific journals will not reveal the identity of the patients. Data retrieved (case report forms, surgery reports, discharge summaries, laboratory and test reports, etc.) from the site will identify patients by their patient number / patient name code only.

#### **CLINICAL ENDPOINT COMMITTEE**

A Clinical Endpoint Committee (CEC) is responsible for adjudicating all SAEs including device deficiencies which may lead to SAE through the 36 month follow-up. In addition all confirmed SAEs are assessed in regards to relationship to the Harpoon device and Index procedure.

The Sponsor's Safety Department manages all CEC preparation activities according to an approved CEC Charter.

Adjudicated data is used for a final analysis. If event is not adjudicated, site reported data is used.

#### **STUDY ADMINISTRATION**

Harpoon Medical, Inc. will make necessary efforts to ensure that this study is conducted in compliance with Good Clinical Practices (GCPs) and all applicable regulatory requirements.

#### **Source Documentation**

The Investigator must maintain detailed source documents on all trial patients who are enrolled in the trial or who undergo screening. Source documents include patient medical records, hospital charts, clinic charts, Investigator's patient trial files, as well as the results of diagnostic tests (e.g.,

laboratory tests) kept in an individual patient binder and stored in a secured and locked location and must be made available to the Monitor during site visits.

The following minimum information should be recorded in the patient's medical records:

- The date the patient entered the trial and the patient number
- The trial protocol number and the name of the Sponsor
- The date that informed consent was obtained
- Evidence that the patient meets trial eligibility requirements (e.g., medical history, trial procedures and/or evaluations)
- The dates of all trial related patient visits
- Evidence that required procedures and/or evaluations were completed
- Use of any concurrent medications
- Documentation of specific device used, if any
- Occurrence and status of any Adverse Events
- The date the patient exited the trial, and a notation as to whether the patient completed the trial or was discontinued, including the reason for discontinuation

